15.3 Phase II Stopping Rules

Toxicity will be reviewed on a continuous basis. Early stopping of this trial is calculated based upon the grade 3 seizure rate. It is assumed that a maximum-tolerated seizure rate is 50% and a seizure rate of 33% and or less is acceptable. For each treatment arm (n=20), based on the repeated significance testing (using R function toxbdry) with 80% power and 0.05 overall Type I error, the study will be halted if a treatment-related seizure occurs in the first patient, or both of the first 2 patients, or 3 of the first 4, or 4 of the first 5, or 5 of the first 7, or 6 of the first 9, or 7 of the first 11, or 8 of the first 14, or 9 of the first 16, or 10 of the first 18, or if the 11th treatment-related seizure is observed before the last (20th) patient has completed the trial.

In addition, enrollment will stop and a review will be conducted to determine whether modifications to the protocol are warranted or if the trial should be terminated if 2 patients in either group die or incur life-threatening (grade 4) adverse reactions that are thought to be at least possibly related to study treatment.

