Principal Investigator Signature Page

Principal Investigator:	[name].	
<hr/> Signature of Investigator		Date
<hr/> Printed Name of Investigator		

By my signature, I agree to personally supervise the conduct of this study and to ensure its conduct in compliance with the protocol, informed consent, IRB/HRPO procedures, the Declaration of Helsinki, ICH Good Clinical Practices guidelines, and the applicable parts of the United States Code of Federal Regulations or local regulations governing the conduct of clinical studies.
		

[figure not shown]
A Phase I/II Study Testing the Safety, Toxicities, and Efficacy of MK-3475 in Combination with MRI-guided Laser Ablation in Recurrent Malignant Gliomas

SCHEMA

Phase I sample size: maximal 18
Phase II sample size: 32 evaluable patients with up to 39 enrollments

Dose Escalation Schedule (Phase I portion)	
Dose Level	MK-3475 Dose
Level 1 (Starting Dose)	100 mg IV q3wks
Level 2	150 mg IV q3wks
Level 3	200 mg IV q3wks

As of Amendment 12, patients will no longer be randomized in the phase II portion of this trial. Phase II patients enrolled after the approval of Amendment 12 will participate in a single treatment arm with MK-3475 and MLA and follow the schedule of events in Section 10.2.1 of the protocol.

Glossary of Abbreviations

AE	Adverse event
ALT (SGPT)	Alanine transaminase (serum glutamate pyruvic transaminase)
ANC	Absolute neutrophil count
AST (SGOT)	Aspartate transaminase (serum glutamic oxaloacetic transaminase)
BBB	Blood brain barrier
B-HCG	Beta human chorionic gonadotropin
CBC	Complete blood count
CFR	Code of Federal Regulations
CNS	Central nervous system
CRF	Case report form
CT	Computed tomography
CTCAE	Common Terminology Criteria for Adverse Events
CTEP	Cancer Therapy Evaluation Program
DLTs	Dose Limiting Toxicities
DSM	Data and Safety Monitoring
ECI	Event of clinical interest
FDA	Food and Drug Administration
FNA	Fine needle aspiration
FWA	Federal wide assurance
GBM	Glioblastoma multiforme
HIV	Human Immunodeficiency Virus
HRPO	Human Research Protection Office (IRB)
IB	Investigator's brochure
IHC	Immunohistochemistry
IND	Investigational New Drug
INR	International normalized ratio
irAE	Immune-related adverse event
IRB	Institutional Review Board
IULN	Institutional upper limit of normal
IV	Intravenous (i.v.)
MLA	MRI-guided laser ablation
MRI	Magnetic resonance imaging
MTD	Maximum tolerated dose
NCI	National Cancer Institute
NIH	National Institutes of Health
NSCLC	Non-small cell lung cancer

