7.0 REGULATORY AND REPORTING REQUIREMENTS

The entities providing oversight of safety and compliance with the protocol require reporting as outlined below. Please refer to Appendix B for definitions and Appendix C for a grid of reporting timelines.

Adverse events will be tracked from start of treatment through 30 days following the last day of study treatment. SAEs will be tracked for 90 days following the last dose of study treatment. All adverse events must be recorded on the toxicity tracking case report form. This includes all adverse events:

- belonging to the category “Nervous System Disorders” in the CTCAE version 4.03, regardless of attribution
- experienced by the patient during the administration of MK-3475, regardless of attribution
- that are CTCAE version 4.03 gradable laboratory values, regardless of attribution

The only adverse events that will not be recorded are adverse events that are clearly related to MLA and/or surgery AND ALSO not related to MK-3475.

Refer to the data submission schedule in Section 11 for instructions on the collection of AEs in the EDC.

Reporting requirements for Washington University study team may be found in Section 7.1. Reporting requirements for secondary site study teams participating in Washington University-coordinated research may be found in Section 7.3.

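### The Phase II seizure stopping rule has a Type I error of about 0.39 and power of about 0.73, not the stated 0.05 and 80%, and it ends at patient 20 of an arm that now runs to 32

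*Combined protocol and SAP*

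**What the plan says.** Section 15.3 bases early stopping on seizures. Its two reference rates are these: "a maximum-tolerated seizure rate is 50% and a seizure rate of 33% and or less is acceptable". The method and size are given as: "For each treatment arm (n=20), based on the repeated significance testing (using R function toxbdry". The claimed properties and the first boundary point are in one sentence: "with 80% power and 0.05 overall Type I error, the study will be halted if a treatment-related seizure occurs in the first patient". The remaining points are 2 of 2, 3 of 4, 4 of 5, 5 of 7, 6 of 9, 7 of 11, 8 of 14, 9 of 16 and 10 of 18. The last is an 11th seizure before the 20th patient completes. Monitoring is continuous: "Toxicity will be reviewed on a continuous basis".

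The Schema gives the current design: "Phase II sample size: 32 evaluable patients with up to 39 enrollments". Section 15.4 shows how this arises: 12 patients already in the combination group (2 from Phase I, 10 from Phase II), plus 27 more enrolled of whom 20 are expected to be evaluable. Section 15.3 still speaks of each arm and of either group.

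On data capture, Section 7.0 calls for nervous-system events to be recorded whatever their attribution, but it also leaves out "adverse events that are clearly related to MLA and/or surgery AND ALSO not related to MK-3475".

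**The concern.** A rule that halts on a single event in the first patient has a false-halt probability at least equal to the event rate. With an acceptable rate of 33%, that cannot be squared with an overall error of 0.05. The first-patient clause also leaves the next one, both of the first 2, with nothing to do.

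The rule is the plan's only quantitative seizure guard, and Section 13.0 requires the stopping rules and supporting data to be included in the monitoring report. If its error rates are wrong, the DSMB is working with properties the rule does not have. If it ends at patient 20, the DSMB has no seizure boundary for the later patients.

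There is a lesser problem with the input. The rule is said to rest on the grade 3 seizure rate, but its clauses count treatment-related seizures with no grade. A seizure clearly due to MLA and not to the drug is related to the tested combination, yet the Section 7.0 exclusion would leave it unrecorded.

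**Working it through.** **Inputs.** All are from Section 15.3: acceptable rate 0.33, maximum tolerated rate 0.50, n = 20, review after every patient, and the printed boundary. The smallest seizure count that halts the study at patients 1 to 20 is 1, 2, 3, 3, 4, 5, 5, 6, 6, 7, 7, 8, 8, 8, 9, 9, 10, 10, 11, 11.

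**Lower bound by hand.** P(halt at patient 1) = p, which is 0.33 at the acceptable rate. This already exceeds 0.05.

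**Exact recursion.** Let a(i, x) be the probability of reaching patient i with x seizures and no halt, and b(i) the halting count. Then a(i, x) = (1 − p)·a(i−1, x) + p·a(i−1, x−1) for x < b(i). The mass falling at x ≥ b(i) is the probability of halting at patient i.

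| Halt at patient | p = 0.33 | p = 0.50 |
|---|---|---|
| 1 | 0.3300 | 0.5000 |
| 4 | 0.0241 | 0.0625 |
| 7 | 0.0053 | 0.0234 |
| 9 | 0.0047 | 0.0234 |
| 11 | 0.0037 | 0.0210 |
| 13 | 0.0029 | 0.0184 |
| 14 | 0.0067 | 0.0324 |
| 16 | 0.0038 | 0.0205 |
| 18 | 0.0026 | 0.0162 |
| 20 | 0.0020 | 0.0135 |
| **Total** | **0.386** | **0.731** |

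For example, the patient-4 entry at 33% is a seizure-free first patient followed by three seizures: 0.67 × 0.33³ = 0.0241. No other patient number can be the halting point. Taking the acceptable rate as 1/3 gives 0.391. A simulation of 400,000 trials per rate gave 0.385 and 0.732. The plan's 0.05 and 0.80 are not reproduced.

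**Other readings of the boundary.**

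| Reading | Type I error | Power |
|---|---|---|
| As printed | 0.386 | 0.731 |
| 11th seizure needed by patient 19 | 0.384 | 0.718 |
| Without 1 of 1 | 0.205 | 0.632 |
| Also without 2 of 2 | 0.163 | 0.603 |
| Also without 3 of 4 | 0.116 | 0.565 |
| Single look, 11 of 20 | 0.035 | 0.412 |

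None gives 0.05 and 0.80 together.

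**Could any rule meet the claim?** A sequential rule on 20 patients is a test based on 20 binary outcomes, so the Neyman-Pearson bound applies. At n = 20, P(X ≥ 11) is 0.0350 at 33% and 0.4119 at 50%; P(X ≥ 10) is 0.0866 and 0.5881. The level-0.05 most powerful test halts at 11 or more, and at exactly 10 with probability (0.05 − 0.0350)/(0.0866 − 0.0350) = 0.291. Its power is 0.4119 + 0.291 × (0.5881 − 0.4119) = 0.463. The same calculation at n = 32 gives 0.625. The smallest single-look exact design meeting both targets has 56 patients (25 or more events: error 0.046, power 0.825).

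**Coverage.** The last boundary point is at patient 20. On the Schema's count, 32 − 20 = 12 evaluable patients, or 39 − 20 = 19 enrolled, lie beyond it. Setting aside the two Phase I patients, the arm has 10 + 20 = 30 evaluable and 10 + 27 = 37 enrolled, leaving 10 and 17 uncovered. With no boundary after patient 20, the probabilities of halting in the larger arm stay at 0.386 and 0.731.

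**The case against.** The strongest objection is timing. By June 2019 the combination arm already had 10 Phase II patients, and Amendment 12 continued accrual, so the early clauses concern patients already enrolled. Of the 0.386, 0.364 falls within the first 10 patients. Given no halt by then, and averaging over seizure counts the documents do not report, the remaining probability of halting by patient 20 is (0.386 − 0.364)/(1 − 0.364) = 0.034 at 33%. This stands as a description of what lies ahead: the risk of a false halt is mostly past. The same calculation at 50% gives (0.731 − 0.609)/(1 − 0.609) = 0.31, so what remains is weak detection, and after patient 20 none. The printed error rates are wrong either way.

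Second, other safeguards exist. Section 15.3 stops enrollment for review after 2 deaths or grade 4 reactions at least possibly related to treatment, with no patient limit, and Section 13.0 requires DSMB meetings at least every six months. Both remain in force, but neither supplies a boundary for grade 3 seizures.

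Third, the event wording can be read charitably, with the later phrase taken to mean the grade 3 event named at the start. The Section 7.0 exclusion is also narrow, since it needs both a clear link to MLA or surgery and no link to MK-3475. Both points are fair. They make the definition a matter for clarification, and they leave the arithmetic untouched.

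Finally, the boundary function named in the plan could not be run for this check. The result does not depend on it, because the printed rule is the one to be applied.

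**Conclusion.** The concern holds. For 33% against 50% with 20 patients, the printed rule has a Type I error of 0.386 against the stated 0.05, and power of 0.731 against the stated 0.80. It is worse than stated in both directions: before any patient is enrolled, it would halt an acceptable regimen more than a third of the time and miss the maximum tolerated rate about a quarter of the time (1 − 0.731 = 0.269). Most of the excess error comes from the first-patient clause, but removing that clause still leaves 0.205, and no boundary of this size could meet both targets. Separately, 10 to 12 evaluable patients in the current arm have no seizure boundary.

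These figures assume independent patients with a common seizure rate, assessment after each patient in order, and the boundary exactly as printed. They do not depend on which seizure definition is meant. The correction must be made, because the text misstates how a safety rule behaves and does not match the current design.

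**What to change.** 1. Rerun the boundary for the single MK-3475 + MLA arm at its current size, stating whether the two Phase I patients count. Print the boundary through the last patient with its exact probability of halting at 33% and at 50%. At 32 patients no level-0.05 rule exceeds 62% power for these rates, so the achieved values must be reported in place of the 0.05 and 80% targets.
2. If the printed boundary is kept for the first 20 patients, replace the stated figures with 0.39 and 0.73. This corrects the text but does not close the gap after patient 20.
3. Reconcile the first-patient clause with whatever error rate is claimed, and update the references to each arm and either group.
4. State one event, either grade 3 or any treatment-related seizure, say whether relatedness includes MLA, and make Section 7.0 record every seizure that feeds the rule.

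The choice of rates and boundary stays with the investigators and the DSMB. The cost is one recalculation and revised wording in Sections 15.3 and 7.0. No patients are added, but the stated operating characteristics will look less favourable.

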15.4 Interim Analysis

Per DSMC request, an interim analysis was conducted in June 2019. The MK-3475 + MLA group included 2 GBM patients who received 200mg in Phase 1 and 10 patients in Phase 2. PFS probability at 6, 9, and 12 months after treatment are 45.0%, 45.0%, and 33.8%, the median PFS is 5.49 months. Survival probabilities at 6, 9, and 12 months after treatment are 75.0%, 62.5%, and 50.0%, and the median OS is not estimable. For the MK-3475 monotherapy (no MLA) group, PFS probability at 3 months after treatment is 44.4%

and the median PFS is 2.73 months (95% CI: 1.41-3.88). Survival probabilities at 3 and 6 months after treatment are 83.3%, and 31.3%, and the median OS is 4.77 months (95% CI: 1.74-8.78).

This analysis showed significant differences in PFS and survival probabilities between the MK-3475 + MLA group and the MK-3475 alone group. Therefore, with Amendment 12, we are revising the study to a single arm (MK-3475 + MLA) in the spirit of minimizing harm, potential or perceived, to subjects and to complete the study in a timely manner. The recent study⁴⁶ shows median PFS was 2.4 months. To be conservative, we will use the shorter mPFS for MK-3475 + MLA group and longer mPFS from historical data. We will enroll additional 27 patients and expect 20 GBM patients will be evaluable for this study. With an accrual interval of 20 months and additional follow-up of 6 months, a two-sided, one-sample logrank test calculated from a sample of 32 subjects achieves 80.9% power at a 0.05 significance level to detect a median PFS of 5.1 months in the MK-3475 + MLA group when the median PFS of the historical control is 2.9 months.

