2.2 Secondary Objectives

1. Phase I: To determine the toxicity profile of MK-3475 in combination with MLA for the treatment of recurrent malignant gliomas.
2. Phase II: To determine the overall survival (OS) of patients with recurrent GBM, WHO grade IV being treated with MK-3475 plus MLA as compared to historical controls treated with MK-3475 alone.
3. Phase II: To assess the anti-glioma immune response before and after MK-3475 with MLA.
4. Phase II: To correlate intratumoral expression of PD-L1 and the frequency of glioma cell-specific cytotoxic T cells with PFS and OS.
5. Phase II: To identify PD-1-dependent biomarkers in glioma cell-specific T cells that negatively correlate with the frequency of glioma cell-specific cytotoxic T cells and PFS and OS.

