4.4 Phase II Patients

As of Amendment 12, patients enrolled in the phase II portion of this trial will no longer be randomized. After registration and surgery (if applicable), these patients will undergo MLA followed by MK-3475 treatment.

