15.2 Analysis Plan

PFS and OS will be estimated by Kaplan-Meier product limit method and the difference in PFS with recurrent GBM being treated with MK-3475 alone vs. those being treated with MK-3475 plus MLA will be compared by log-rank test.

Two-group t-test will be used to compare the anti-glioma immune response before and after MK-3475 with or without MLA.

Cox proportional hazard model will be used to determine the relationship between intratumoral expression of PD-L1, the frequency of glioma cell-specific cytotoxic T cells with PFS and OS while proportional hazard assumption will be examined.

Pearson correlation coefficient (r) will be calculated between intratumoral expression of PD-L1 and the frequency of glioma cell-specific cytotoxic T cells. Similarly, Cox proportional hazard model will be used to investigate the relationship between PD-1-dependent biomarkers in glioma cell-specific T cells and PFS and OS.

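### After Amendment 12 no stated analysis is limited to the concurrently randomised Phase II patients, so a randomised estimate of what MLA adds is not guaranteed for PFS and not planned for OS

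*Combined protocol and SAP*

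**What the plan says.** **Randomisation.** The Schema and sections 1.7 and 4.4 show that Phase II was randomised until Amendment 12. From then on, "patients enrolled in the phase II portion of this trial will no longer be randomized".

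**Sized final test (15.4).** For an accrual of 20 months plus 6 months of follow-up, "a two-sided, one-sample logrank test calculated from a sample of 32 subjects achieves 80.9% power". The level is 0.05, and the contrast is a median PFS of 5.1 months against a historical 2.9 months. On accrual: "We will enroll additional 27 patients and expect 20 GBM patients will be evaluable for this study".

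**June 2019 interim (15.4).** On composition: "The MK-3475 + MLA group included 2 GBM patients who received 200mg in Phase 1 and 10 patients in Phase 2". On the result: "This analysis showed significant differences in PFS and survival probabilities between the MK-3475 + MLA group and the MK-3475 alone group". The next sentence moves to a single arm as a consequence. The section gives PFS and OS figures for the MK-3475-alone group, but not its size, and no test, p-value or hazard ratio.

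**Analysis plan (15.2).** PFS and OS are estimated by Kaplan-Meier. For PFS, patients "being treated with MK-3475 alone vs. those being treated with MK-3475 plus MLA will be compared by log-rank test". No population is named for that test, and no between-arm test of OS is listed.

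**Objectives.** The primary Phase II objective (2.1) names no comparator. The OS objective (2.2) is framed "as compared to historical controls treated with MK-3475 alone", and section 1.7 likewise sets survival endpoints against historical data.

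**The concern.** Sections 1.5, 15.1 and 15.2 all turn on what MLA adds to MK-3475. The patients allocated by randomisation before Amendment 12 are the part of the trial in which the two groups do not differ systematically in how or when they were selected. Phase I patients were not randomised. Patients enrolled after Amendment 12 knew that they would receive MLA and came later, when the control arm had closed. If they enter a between-arm contrast, any prognostic difference between them and the earlier patients is attributed to MLA.

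No passage ties any comparison to the randomised patients. Two statisticians following 15.2 could therefore run quite different contrasts and both be within the plan, and for OS neither would be asked to use the trial's own control arm.

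**Working it through.** **1. The plan's own figure.** Inputs from 15.4: n = 32, medians 5.1 and 2.9 months, two-sided 0.05, 20 months' accrual and 6 months' follow-up. Assume exponential PFS and uniform accrual.

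- Hazard ratio = 2.9/5.1 = 0.569.
- Event probability under the alternative: ω1 = 0.848. Expected cumulative null hazard per patient: ω0 = 0.848/0.569 = 1.491.
- Exact variance under the alternative: σ² = ω1 − ω1² + 2p00 − ω0² − 2p01 + 2ω0ω1, where p00 and p01 are the integrals of G(t)S1(t)·λ0²t and G(t)S1(t)·λ0λ1t. G is the probability of still being under observation and S1 is survival under the alternative. With p00 = 1.859 and p01 = 1.057, σ² = 2.038 and σ = 1.428.
- Power = Φ[(√n(ω0 − ω1) − 1.96√ω0)/σ] = Φ[(3.639 − 2.394)/1.428] = Φ(0.872) = 80.9%.

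The stated power reproduces. No patient on MK-3475 alone contributes to it.

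**2. Who is in the combination group.**

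| Analysis | Combination group | Not randomised |
|---|---|---|
| June 2019 interim (15.4) | 2 Phase I + 10 Phase II = 12 | 2/12 = 17% |
| Final set of 32 (15.4) | 12 + 20 after Amendment 12 | 22/32 = 69% |
| 15.2 log-rank, all treated | as the final set | about 69% |
| 15.2 log-rank, randomised only | 10 | 0 |

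The 12 + 20 make-up of the 32 is inferred because the numbers match. That all 10 Phase II combination patients were randomised is also inferred.

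**3. Which reading of 15.2 the text supports.** For the pooled reading: 15.2 groups patients by the treatment received, and the only composition given anywhere for the combination group is the pooled one in 15.4. For the randomised reading: 15.1 still describes two arms of 20, and 15.2 fits that design left unedited. The text does not settle it.

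**4. Precision of a randomised-only PFS comparison.** Ten combination patients against k controls. The documents do not give k, so 6 to 20 is assumed. The medians are the plan's.

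- Schoenfeld, every patient having an event (upper bound): power = Φ(√(10k/(10 + k))·|ln 0.569| − z).
- k = 6: √3.75 × 0.565 = 1.093. Power is Φ(1.093 − 1.960) = 19% at two-sided 0.05, or Φ(1.093 − 1.036) = 52% at one-sided 0.15.
- k = 20: √6.667 × 0.565 = 1.458. Power is 31% or 66%.
- Simulated log-rank with censoring uniform on 6-26 months, k from 6 to 20: about 20-26% at two-sided 0.05 and about 50-62% at one-sided 0.15.
- Approximate 95% CI around a hazard ratio of 0.569, as exp(ln 0.569 ± 1.96√(1/10 + 1/k)): 0.21-1.56 for k = 6 and 0.26-1.23 for k = 18.

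Both levels are shown because the plan's only level for a two-group PFS test is one-sided 0.15 (15.1), while 15.4 uses two-sided 0.05 for the one-sample test.

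**5. OS.** The log-rank sentence in 15.2 covers PFS only, and 2.2 and 1.7 name historical comparators. On either reading of 15.2, no between-arm OS comparison is planned.

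**The case against.** The strongest reply is that the historical comparator is an openly stated design decision. Amendment 12 turned Phase II into a single-arm study, the primary objective names no comparator, and omitting a supportive two-arm analysis from such a study is not in itself an error. This stands, and it is why the point concerns a supportive analysis and leaves the primary test alone.

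A reader might infer that 15.2 definitely pools non-randomised patients, so that the randomised estimate will never be produced. The documents do not support that. Section 15.2 defines no analysis set, and the sentence naming the 2 Phase I patients describes only the June 2019 analysis. Read with 15.1, the 15.2 test may be the randomised comparison left unchanged.

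A reader might also infer that the 80.9% is being claimed for a between-arm comparison. It is not: 15.4 attaches it to the one-sample test.

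Three further cautions hold. First, any figure for the bias from pooling needs an assumed prognostic difference, and the documents give neither its size nor its direction, so none is claimed here. Second, the randomised comparison is small whichever level is used. Third, it is not automatically free of bias. Section 12.3.6 counts PFS from start of treatment, and under section 5.0 the sequence from surgery to first study treatment differs with and without MLA, so the time origin must be fixed.

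Low precision is no reason to omit the estimate. A hazard ratio with a wide interval helps a reader to weigh the difference reported in 15.4.

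**Conclusion.** The point holds in this form. Three facts are explicit: the one-sample test omits the MK-3475-alone arm, the June 2019 combination group included 2 non-randomised patients among 12, and no between-arm OS test is planned. No passage restricts a comparison to concurrently randomised patients. A randomised PFS estimate is therefore left to interpretation of 15.2, and a randomised OS estimate is absent.

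Under the all-treated reading, about 22 of 32 combination patients (69%) would be non-randomised. Under the randomised reading, the contrast is about 10 against an unstated number of controls, with the limited power shown above. These sizes rest on the inferred make-up of the 32, the inference that all 10 Phase II combination patients were randomised, an assumed 6 to 20 controls, and exponential PFS at the plan's medians. The primary objective, the sample size and the 80.9% are unaffected.

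**What to change.** **In 15.2:**
- State the population of the two-group PFS comparison.
- Add a supportive PFS and OS analysis limited to patients randomised before Amendment 12, excluding Phase I and post-amendment patients. Analyse them as randomised, with follow-up to the final data cut and one time origin common to both arms (for example, randomisation). Report a log-rank test and a Cox hazard ratio with 95% CI.
- Label any contrast that includes Phase I or post-amendment patients as non-randomised and descriptive.
- Describe the randomised comparison as imprecise, without a fixed power figure, since that would depend on the control number and the level chosen.

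**In 15.4:** report the June 2019 between-arm result with and without the 2 Phase I patients, and give the number of control patients.

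**Cost:** some wording and one extra analysis of data already collected, with no new patients or procedures. The downside is a wide interval that may look less favourable than the interim statement.

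### The one-sample log-rank form that reproduces the 80.9% power is conservative for benefit at n=32 (about 1.7% against a nominal 2.5%); name the statistic in 15.2/15.4 and use the (O+E)/2 variance

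*Combined protocol and SAP*

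**What the plan says.** PFS is the phase II primary objective (section 2.1). After the change to a single arm, section 15.4 gives the power: "a two-sided, one-sample logrank test calculated from a sample of 32 subjects achieves 80.9% power at a 0.05 significance level". The medians behind that figure are 5.1 months for the combination and 2.9 months for the historical control. The timing is "With an accrual interval of 20 months and additional follow-up of 6 months".

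The 32 patients are made up of 12 already in hand ("The MK-3475 + MLA group included 2 GBM patients who received 200mg in Phase 1 and 10 patients in Phase 2") and 20 more ("We will enroll additional 27 patients and expect 20 GBM patients will be evaluable for this study"). The Schema agrees: "Phase II sample size: 32 evaluable patients with up to 39 enrollments".

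No section gives the variance used in the one-sample statistic or its critical value. Section 15.2, the analysis plan, still describes a comparison of two groups: "MK-3475 alone vs. those being treated with MK-3475 plus MLA will be compared by log-rank test".

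**The concern.** The one-sample log-rank test compares observed events O with E, the number expected if the patients followed the historical curve. The usual form divides E-O by sqrt(E). When patients do well they stay at risk longer, so E grows and the larger denominator pulls Z back towards zero. When they do badly E shrinks, and Z is pushed outwards. With about 30 events this asymmetry is not negligible, and a nominal two-sided 0.05 need not mean 0.025 on each side.

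The trial asks whether PFS improves. If the benefit tail falls well short of 2.5%, the design gives up power that it could have with the same patients. Section 15.2 also leaves the statistic open, so it could be chosen after the data are seen.

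**Working it through.** **Inputs (section 15.4).** n = 32; null median 2.9 months; alternative median 5.1 months; accrual 20 months; further follow-up 6 months; two-sided alpha 0.05. Assumed, because the documents do not say: exponential PFS, uniform accrual (so censoring is uniform on 6 to 26 months), and a null median known without error.

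**Step 1: reproduce the stated power.**
- Hazards: λ0 = ln2/2.9 = 0.2390; λ1 = ln2/5.1 = 0.1359; hazard ratio 2.9/5.1 = 0.569.
- Event probability: 1 - exp(-6λ)·(1 - exp(-20λ))/(20λ). This is 0.848 under the alternative (32 × 0.848 = 27.1 events) and 0.951 under the null (32 × 0.951 = 30.4 events).
- Per patient under the alternative: observed v1 = 0.8480; null-expected v0 = 0.8480 × 5.1/2.9 = 1.4913.
- Variance of O-E per patient: σ² = v1 - v1² + 2·v00 - v0² - 2·v01 + 2·v0·v1. Here 2·v00 is the mean squared null cumulative hazard (v00 = 1.8593), and v01 = 1.0572 is the mean of the event indicator times that hazard. So σ² = 0.8480 - 0.7191 + 3.7186 - 2.2239 - 2.1145 + 2.5291 = 2.038, and σ = 1.428.
- Variance E: power = Φ[(√32 × 0.6433 - 1.96 × √1.4913)/1.428] = Φ[(3.639 - 2.393)/1.428] = Φ(0.872) = 80.85%.

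This matches the stated 80.9%, and 32 is the smallest n that reaches 80%. Other forms at n = 32 do not match: (O+E)/2 variance 85.6%; log hazard ratio 83.7%; variance E with a simpler alternative SD 91.2%; variance E at one-sided 0.05, 87.3%.

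**Step 2: the mechanism, at the design's own expected values.** Under the alternative, O = 27.1 and E = 32 × 1.4913 = 47.7.
- Variance E: Z = 20.6/√47.7 = 2.98.
- Variance (O+E)/2: Z = 20.6/√37.4 = 3.36.

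**Step 3: simulated tails and power** (1,000,000 trials per scenario; cut-offs ±1.96).

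| n = 32 | Variance E | Variance (O+E)/2 |
|---|---|---|
| Null 2.9 months, reject for benefit | 1.7% | 2.5% |
| Null 2.9 months, reject for harm | 3.7% | 2.4% |
| Total | 5.4% | 4.9% |
| Power at 5.1 months | 84.0% | 87.1% |

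With (O+E)/2 variance, 29 patients give about 84%, so the gain is worth about three evaluable patients. On the design formula, the same change moves 80.9% to 85.6%.

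**Step 4: sensitivity** (benefit/harm tails, variance E then (O+E)/2).
- 12 patients followed longer: 1.69%/3.71%, then 2.49%/2.41%; power gain 2.9 points.
- Assumed 10% dropout by 6 months: 1.69%/3.70%, then 2.52%/2.37%; gain 3.8 points.
- No censoring: 1.66%/3.73%, then 2.41%/2.43%; gain 2.4 points.
- Everyone censored at 6 months (extreme): 1.75%/3.58%, then 2.79%/2.25%; gain 6.2 points.

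**Step 5: where the gain comes from.** If both statistics are calibrated to exactly 2.5% for benefit, each has power of about 87.0%. The gain is recovered alpha. Its counterpart is on the harm side: at an assumed true median of 2.0 months, rejection for harm falls from 57% to 49%.

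**The case against.** The strongest reply is that section 15.4 contains no error: it gives a correctly computed power for an accepted test. That stands. A reader might infer that the trial is underpowered or that 80.9% is wrong. The documents do not support this, because the figure reproduces and the simulated power of that test is about 84%, above the figure claimed. Nor would a positive result under the standard statistic be invalid, since its benefit-side error is below nominal.

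Second, matching 80.9% identifies the formula used for sample size. It does not show which statistic will be run. That also stands: the variance form is an inference, and section 15.2 names no one-sample test at all. It is a reason to specify the statistic.

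Third, the change could be presented as free. It adds no patients and keeps total error within 5%, but it spends more alpha on benefit and gives up harm-side rejection. The rejection given up comes from a tail that was above its nominal 2.5%. The toxicity stopping rules in section 15.3 are separate and unaffected.

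Fourth, the null is not known. Section 15.4 itself cites 2.4 months from a recent study and 2.73 months (95% CI 1.41-3.88) from the trial's own monotherapy group. If the true control median were 3.3 months (an assumption), the benefit-side error would be 8.9% with variance E and 11.7% with (O+E)/2. In addition, 12 of the 32 patients had been seen at the interim that led to the single-arm design. These problems affect both statistics and need their own answer. Restoring 2.5% under a fixed null must not be read as controlling the trial's overall false-positive risk.

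**Conclusion.** The point holds as a modest, cheap improvement. The stated 80.9% is right for the standard statistic. At n = 32 that statistic is lopsided: about 1.7% for benefit and 3.7% for harm, 5.4% in total. The (O+E)/2 variance brings the tails to about 2.5% and 2.4% and raises simulated power by about 3 points, from about 84% to about 87%.

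This rests on exponential PFS, uniform accrual and a null median fixed at 2.9 months. The tail pattern was stable under the follow-up and censoring variations tried. That variance E is the intended form is inferred from the power figure alone. The firmer finding is that no section specifies the one-sample statistic for the primary endpoint.

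**What to change.** Before the final PFS analysis, state in sections 15.2 and 15.4 that the primary PFS test is the one-sample log-rank against the historical control. Give the statistic as Z=(E-O)/sqrt((O+E)/2), with E the expected events under the historical curve, tested two-sided at 0.05. This should replace or sit beside the two-group wording in 15.2.

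For power, either keep 80.9% and label it as the standard-formula figure with variance E, or give about 87% by simulation and state the assumptions (exponential PFS, uniform accrual, fixed 2.9-month null).

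Say openly that harm-side rejection returns to its nominal level. The cost is a line or two of text, with no change to patients, data or procedures. Uncertainty in the 2.9-month median needs separate treatment.
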